### 3. ENDPOINTS

#### 3.1 Primary Endpoint(s)

**Acute pain:** The primary endpoint for the acute pain study is the SIA score, a composite of pain and opioid usage, at 10 days post-surgical procedure. See Appendix A for the SIA score rationale.

**Chronic pain:** The primary endpoint for the chronic pain study is change in composite pain intensity score, assessed using the PROMIS pain intensity survey, from baseline to 3 months post return of genetic testing results to the provider.

**Depression:** The primary endpoint for the depression study is change in depression score, assessed using the PROMIS Emotional Distress - Depression 8b survey (adults) or PROMIS pediatric depressive symptoms (pediatric), from baseline to 3 months post return of genetic testing results to provider.

#### 3.2 Secondary Endpoints

Secondary endpoints include:

##### All Trials

1. Overall well-being at 6-month follow-up
2. Sub-domains of overall well-being: pain interference, physical function, sleep disturbance, social role and activities functioning, fatigue, anxiety, and depression at 6-month follow-up
3. Concordance between metabolizer phenotype and prescribed medication

##### Acute pain

1. Pain intensity at 10 days post-surgery
2. Opioid usage at 10 days post-surgery
3. Prescription pain medication misuse score at 3-months post-surgery
4. Mobility at 1-month post-surgery
5. Opioid persistence 6 months post-surgery

##### Chronic pain

[figure not shown]
1. Pain reduction magnitude at 3-month post return of genetic testing results to provider, relative to baseline
2. Proportion of participants achieving clinically significant pain reduction (30% reduction from baseline) at 3-months post return of genetic testing results to provider
3. Prescription pain medication misuse at 3-months post return of genetic testing results to provider

##### Depression

1. Change in PHQ-8 score between baseline and 3 months
2. Achieve 50% reduction in PHQ-8 scores at 3 months, relative to baseline
3. Medication side effects severity burden at 3 months
4. Participant medication adherence at 3 months
5. Achieve remission at 6 months, defined as PROMIS depression score  $\leq 16$
6. Achieve remission at 6 months, defined as PHQ-8 score  $\leq 4$

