#### Depression

Age  $\geq$  8 years

- English speaking or Spanish speaking
- Patients followed at psychiatry clinics or primary care clinics at an enrolling site (such as, but not limited to, Internal Medicine, Family Medicine, or Pediatrics)
- Documentation of depression and/or provider report of depression
- Evidence of depressive symptoms for at least 3 months based on patient interview or documentation in electronic health records
- Recent initiation of SSRI therapy, recent revised SSRI therapy, or anticipate need for revised or new SSRI therapy per health care provider

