### Depression

The effect of genotype guided antidepressants therapy on the secondary endpoint depression remission and achieving 5% reduction in PHQ-8 scores will be assessed by comparing the Intervention group subset with CYP2D6 UM or PM or CYP2C19 UM, RM, or PM phenotypes the

Control group subset with CYP2D6 UM or PM or CYP2C19UM, RM, or PM phenotypes using a test of two-proportions with an alpha of 0.05. The effect of genotype guided antidepressants therapy on the secondary endpoints, medication adherence, PHQ-8 scores, and medication side effect severity burden, will be assessed by comparing the Intervention group subset with CYP2D6 UM or PM or CYP2C19 UM, RM, or PM phenotypes the Control group subset with CYP2D6 UM or PM or CYP2C19 UM, RM, or PM phenotypes using a two-sided Mann Whitney test with an alpha of 0.05. Participants that do not have metabolizer phenotypes will not be included in these analyses.

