### 11.2 Data Element Definitions

Clinically significant pain reduction: Whether or not the pain reduction score is  $\leq 0.7$ . If the pain reduction score is  $\leq 0.7$ , clinically significant pain reduction is achieved, if pain reduction scores is  $> 0.7$ , clinically significant pain reduction is not achieved.

Depression symptom control: The change in the PROMIS Emotional Distress - Depression 8b or PROIMIS pediatric Depression 8a survey depression score from baseline to time t.

Depression remission: A. Whether or not the summed raw PROMIS emotional distress depression 8b survey responses are  $\leq 16$ , which is equivalent to the participant responding “rarely” or “never” to most or all of the PROMIS emotional distress - depression 8b survey questions. B. Whether or not the PHQ-8 scores are  $\leq 4$ , which is equivalent to depression severity being none-mild.

Depression (PHQ-8) score: The sum of the responses to the PHQ-8 survey, range from 0 to 24.

Depression (T) score: The T-score converted summed responses to the PROMIS emotional distress depression 8b survey. The T-score conversion is centered around 50 with standard deviation of 10.

Depression severity: The depression score converted to depression severity (none, mild, moderate, severe) based on the scoring guide for the PROMIS emotional distress depression 8b survey.

Medication adherence: The scored responses to the Voils Medication Adherence survey.

Medication concordance: Whether or not the medication the participant is prescribed after the intervention is concordant with the participants CYP2D6 and, for the depression trial, CYP2C19 phenotype.

Medication side effects severity burden: (Depression only) The sum of the scored severity (none = 0, mild = 1, moderate = 2, severe = 3) for common SSRI side effects.

Opioid misuse score: The T-score converted summed responses to the PROMIS prescription medication misuse 7a survey. The T-score conversion is centered around 50 with standard deviation of 10.

Opioid persistence: Defined as  $\geq 1$  opioid prescription refill between 90 days and 180 days after the surgical procedure.

Opioid usage: The average daily morphine equivalents in mg (MED) in past 7 days. MEDs will be calculated using data from the opioid usage survey.

Overall well-being: Defined as the T-score converted summed responses to the PROMIS 43/PROMIS 37 pediatrics survey. The T-score conversion is centered around 50 with standard deviation of 10.

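### Depression remission and 50% PHQ-8 response have no baseline condition, so actionable-phenotype participants already below the cut count as achieving remission and a baseline PHQ-8 of 0 has no defined response

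*Combined protocol and SAP*

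**What the plan says.** Three of the six depression-specific secondary endpoints in Section 3.2 are yes/no outcomes:

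- "Achieve 50% reduction in PHQ-8 scores at 3 months, relative to baseline"
- "Achieve remission at 6 months, defined as PROMIS depression score" of 16 or less
- "Achieve remission at 6 months, defined as PHQ-8 score" of 4 or less

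Section 11.2 defines remission by the score reached. The PROMIS version is a summed raw score on the adult 8b form. The PHQ-8 version is a score of 4 or less, "which is equivalent to depression severity being none-mild". Neither refers to baseline. Section 11.2 gives the PHQ-8 range as 0 to 24 and has no entry for PHQ-8 response.

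The depression criteria in Section 5.1 ask for a diagnosis that may be recorded or simply reported by the provider, for a symptom history ("Evidence of depressive symptoms for at least 3 months based on patient interview or documentation in electronic health records"), and for one of several treatment situations ("Recent initiation of SSRI therapy, recent revised SSRI therapy, or anticipate need for revised or new SSRI therapy per health care provider"). No score threshold appears there or in the exclusions of Section 5.2.

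Section 10.5 compares remission and PHQ-8 response between arms in the actionable-phenotype subset, "using a test of two-proportions with an alpha of 0.05". It has no baseline restriction or adjustment. It also gives the response threshold as 5%, where Section 3.2 and the synopsis give 50%.

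**The concern.** Eligibility rests on a history of depression, not on a current score. The 3 months of symptoms need not be the most recent 3 months; the chronic pain criterion, by contrast, asks for at least the last 3 months. A person who recently started an SSRI and has already improved can enrol.

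For such a person, remission at 6 months means staying where they began. The published proportion would be read as a remission rate while including people who had nothing to remit from. If those people stay below the cut equally often in both arms, they also shrink the difference.

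Response has a separate problem. A percentage reduction from 0 does not exist, and near the floor a change of one or two points decides the outcome. As written, the programmer would have to invent a rule.

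**Working it through.** **The plan's own figure.** A two-sided two-sample t-test with standardized effect 0.28, alpha 0.049 and 90% power needs 270.4, so 271 per arm or 542 in all (power 90.06% at 271). Then 271/0.40 = 677.5, rounded to 678 per arm, and 678/0.90 = 753.3, rounded to 754 per arm, 1508 in all. Section 10.1 reproduces. It concerns the T-score change; no sample size is stated for remission or response.

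**50% response at low baselines (exact).** Response requires follow-up ≤ baseline/2.

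| Baseline PHQ-8 | Highest follow-up score that counts | Fall needed |
|---|---|---|
| 0 | undefined (division by 0) | – |
| 1 | 0 | 1 |
| 2 | 1 | 1 |
| 3 | 1 | 2 |
| 4 | 2 | 2 |

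**Remission (illustration only).** Let f be the share already below the cut at baseline, m the share of those still below it at 6 months, and p the remission rate among those above it. The rate in an arm is f·m + (1 − f)·p, so the difference between arms is f·(mI − mC) + (1 − f)·(pI − pC), with I for intervention and C for control.

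The documents give none of these values. Assumptions: pC = 25%, pI = 37%, f from 5% to 30%. Power uses the normal approximation for two proportions at two-sided alpha 0.05:

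Φ{ [d − 1.96·√(2·p̄(1 − p̄)/n)] / √([pC′(1 − pC′) + pI′(1 − pI′)]/n) }

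Here pC′ and pI′ are the proportions compared, d is their difference and p̄ their mean. For all participants n = 271 per arm; for the restricted analysis n = 271·(1 − f), rounded.

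Example with f = 10% and m = 70% in both arms:
- control 0.07 + 0.90 × 0.25 = 29.5%
- intervention 0.07 + 0.90 × 0.37 = 40.3%
- d = 10.8 points
- power = Φ[(0.108 − 1.96 × 0.04095)/0.04069] = Φ(0.68) = 75%
- restricted (25% v 37%, n = 244): 82%

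| f | Rates, m = 70% in both arms | Difference (points) | Power, all | Power, restricted (n per arm) | Power, all, if m = 70% control v 80% intervention |
|---|---|---|---|---|---|
| 5% | 27.25% v 38.65% | 11.4 | 81% | 84% (257) | 84% |
| 10% | 29.5% v 40.3% | 10.8 | 75% | 82% (244) | 82% |
| 20% | 34.0% v 43.6% | 9.6 | 63% | 77% (217) | 79% |
| 30% | 38.5% v 46.9% | 8.4 | 51% | 72% (190) | 76% |

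With f = 0, power is 86%. If everyone below the cut stays there in both arms, all-participant power at f = 10%, 20%, 30% is 74%, 61%, 50%, so the common level of m matters little. A difference in m between arms matters a great deal, as the last column shows.

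**Labelling.** The share of control-arm remitters already below the cut at baseline is f·m/(f·m + (1 − f)·0.25). With m = 70% this is 0.035/0.2725 = 13%, 0.07/0.295 = 24%, 0.14/0.34 = 41% and 0.21/0.385 = 55% for f = 5%, 10%, 20%, 30%.

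**The case against.** The strongest reply is that remission status at 6 months in the whole actionable set is a coherent pragmatic estimand, in the population used for the other depression-specific endpoints. Better drug or dose selection might also help people stay well, and restriction would discard that effect. At 70% v 80% maintenance the restricted analysis gains nothing at f = 5% or 10% and loses about 2 and 5 points of power at 20% and 30%. This stands: the power argument cannot carry the point alone.

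The share already below the cut may also be small. The objective in Section 2.2 refers to participants who require new or revised therapy. At f = 2% with equal maintenance, power is 84% against 85%, which is negligible. This stands too, although Section 5.1 also admits recent starters.

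Further, these are secondary endpoints with no claimed power, Section 10.9 calls for cautious reading, and change in PHQ-8 is already a secondary endpoint needing no cut. Section 10.2 defers detail to a separate plan for each trial, which may hold a rule for a baseline of 0; the documents at hand contain none.

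A reader might infer that the comparison is biased between arms. The documents do not support that: allocation is randomised, so baseline remitters should fall evenly on average. Nor is everyone randomised scored; Section 10.5 limits these tests to actionable phenotypes.

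**Conclusion.** The point holds as one of definition and labelling, and it is minor. Followed as written, the plan credits people already below the cut with achieving remission, makes responders of people at PHQ-8 1 to 4 on a fall of 1 or 2 points, and cannot score a baseline of 0. These follow from the text without any assumption.

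Dilution is conditional on similar maintenance in the two arms. Its size cannot be derived, because the documents give neither the baseline score distribution nor any remission rate; the power figures illustrate and do not predict. A reader might conclude that the trial is underpowered or that restriction always helps. Neither follows: the primary T-score analysis and its 542 participants are untouched, and the benefit of restriction disappears under a modest maintenance effect.

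**What to change.** In Sections 3.2, 10.5 and 11.2:

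1. Analyse 50% PHQ-8 response in actionable-phenotype participants with baseline PHQ-8 of 5 or more, and add a definition of response to Section 11.2.
2. Analyse each remission endpoint in actionable-phenotype participants above that instrument's own cut at baseline (PHQ-8 above 4; adult PROMIS 8b raw sum above 16).
3. Define these subsets from baseline scores recorded before assignment is known. Section 7.2 places the depression baseline after consent but does not say that it precedes randomisation.
4. State the PROMIS cut for the pediatric 8a form, or on the common T-score scale that Section 10.4 already uses. The raw cut in Section 11.2 is defined only for adult 8b.
5. Keep the all-participant comparison as a sensitivity analysis, labelled as being in remission at 6 months and adjusted for baseline score. Report participants below the cut at baseline separately.
6. Reconcile the 5% in Section 10.5 with the 50% in Section 3.2 and the synopsis.

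The cost is wording, somewhat fewer participants and separate denominators in three secondary analyses. No new data are needed: Table 8 already schedules both instruments at baseline.

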#### 4. Study Arms & Design

This is a prospective, multicenter, subset analysis of 1:1 randomized Intervention (immediate PGx testing and genotype-guided opioid or SSRI therapy with clinical decision support) vs. Control (usual care with delayed PGx testing) pragmatic, open label clinical trial (Figure 1). The three trials are 1) genotype-guided opioid therapy among post-surgical acute pain participants (Acute Pain, Figure 1A), 2) genotype-guided opioid therapy among chronic pain participants (Chronic Pain, Figure 1B), and 3) genotype-guided SSRI therapy in participants with depression (Depression, Figure 1C). Trial-specific outcomes will be compared between participants in the intervention arm and control arms who have an actionable phenotype. Actionable phenotypes are defined as CYP2D6 IM and PMs (i.e. CYP2D6 activity score  $\leq 0.75$ ) for the acute pain and chronic pain trials and CYP2C19 UM, RM and PMs or CYP2D6 UM and PMs for the depression trial.

**Figure 1. ADOPT PGx Trial Design**

Intervention participants are denoted by blue boxes and blue lines, control participants are denoted by orange boxes and orange lines. Return of results are denoted with black outlines, endpoint comparison groups (actionable phenotypes in the control and intervention arms) are denoted with red outlines, and \* denote timing of the primary endpoint collection. Time 0 denotes the time from which the follow-up assessment timing begins.

#### **4.1 Randomization**

After participants provide informed consent/assent, participants will be randomized in a 1:1 allocation to the Intervention (i.e. immediate PGx testing and genotype-guided opioid or SSRI therapy with clinical decision support) and Control (i.e. usual care with delayed PGx testing) arms. Randomization will be stratified by trial and site or clinic with a random block size within each site or clinic. We anticipate variability in patient populations between recruiting sites or clinics and aim to balance the intervention assignments within the site or clinic unit. Additionally, the randomization for the chronic pain trial will be stratified by presence/absence of depression, and the randomization for the acute pain and depression trials will be stratified by pediatric/adult.

The randomization scheme will be generated by an unblinded statistician. Randomization assignments will be generated in real time in REDCap at the Coordinating Center.

#### **4.2 Blinding**

ADOPT PGx randomization assignments will not be blinded to the participants or their providers but will be masked to the UF call center personnel who may be administering some of the participants follow-up surveys. Due to the nature of the intervention, it is impossible to completely mask participants and providers from the pharmacogenetic testing and return of results, hence participants, providers, and local study personnel will not be blinded. While the UF call center personnel administering follow-up surveys will be masked from the results and randomization, study-arm specific questions in the final (6 month) survey may reveal study arm randomization. Additionally, participants may volunteer to reveal their randomization or PGx testing results. If the randomization or phenotype is revealed to the call center, prior to administering the 6 month surveys, it will be documented in the database.

## 5. STUDY POPULATION

### 5.1 Inclusion Criteria

#### Acute Pain

- Age  $\geq$  8 years
- English speaking or Spanish speaking
- Elective/planned surgery types with planned or anticipated to be treated with tramadol, hydrocodone, or codeine pain management at an enrolling site, which may include orthopedic surgeries(e.g. arthroplasty, spine, etc.), open abdominal surgery, or cardiothoracic surgery and others

#### Chronic Pain

- Age  $\geq$  18 years
- English speaking or Spanish speaking
- Seen at primary care clinics at an enrolling site (such as, but not limited to, Internal Medicine, Family Medicine, Pediatrics) or seen in pain-relevant specialty clinics
- History of pain for at least the last 3 months
- Currently treated or being considered for treatment with tramadol, hydrocodone, or codeine to improve pain management

#### Depression

Age  $\geq$  8 years

- English speaking or Spanish speaking
- Patients followed at psychiatry clinics or primary care clinics at an enrolling site (such as, but not limited to, Internal Medicine, Family Medicine, or Pediatrics)
- Documentation of depression and/or provider report of depression
- Evidence of depressive symptoms for at least 3 months based on patient interview or documentation in electronic health records
- Recent initiation of SSRI therapy, recent revised SSRI therapy, or anticipate need for revised or new SSRI therapy per health care provider

### 5.2 Exclusion criteria

#### Trial-wide:

- Life expectancy less than 12 months
- Are too cognitively impaired to provide informed consent/assent and/or complete study protocol
- Are institutionalized or too ill to participate (i.e. mental or nursing home facility or incarcerated)
- Have a history of allogeneic stem cell transplant or liver transplant
- People with prior clinical pharmacogenetic test results for genes relevant for the study in which they will enroll (*CYP2D6* for the pain studies and *CYP2D6* or *CYP2C19* for depression) or already enrolled in an ADOPT PGx trial
- Any other medical, behavioral, or developmental condition that in the opinion of the investigator may confound study data/assessments

#### Acute Pain

- Receiving chronic opioid therapy, defined as use of opioids on most days for  $>3$  months

**Chronic Pain**

- Plan to move out of the area within 6 months of enrollment
- Undergoing treatment for an active cancer diagnosis
- Currently taking daily opioids other than tramadol, codeine or hydrocodone for treatment of pain
- Using a pain pump

**Depression**

- Plan to move out of the area within 6 months of enrollment
- Have active psychosis or diagnosis of a psychotic disorder (schizophrenia, schizoaffective disorder, delusional disorder, psychotic depression, substance induced psychosis, schizophreniform disorder) Have dementia or other neurocognitive disorders due to any cause, such as Alzheimer's disease, vascular/subcortical, lewy body, frontotemporal lobar degeneration
- Have cognitive developmental delay and/or cognitive disability, including autism spectrum disorders (Note: ADHD is not an exclusion criteria)
- Has a seizure disorder
- Have bipolar disorder

## **6. RECRUITMENT AND ENROLLMENT PROCEDURES**

Outlined below are **suggested strategies** for recruitment and enrollment. It is anticipated that each site will need to optimize the strategies that work best for the clinic and patient population and are in accordance with local regulations and procedures. Strategies utilized will be documented for each recruiting site (see MOP for details). Sites shall maintain local recruitment logs per local policies and share aggregated data with the CC.

### **6.1 Provider Recruitment and Assent**

Acute Pain: Providers with a predominant use of codeine, tramadol, and hydrocodone for pain control before and during the 10-day primary endpoint may be approached by qualified study personnel. Providers will be notified per site institutional guidelines that their patients may be contacted by study site recruiters to participate. Surgical procedures where there is persistent pain at the 10-day primary endpoint should be prioritized for inclusion in the study.

Chronic Pain: Primary care providers, pain clinic providers, and/or anesthesiologists specializing in pain control who treat patients meeting eligibility criteria will be identified, and may be approached by qualified study personnel. Providers will be notified per site institutional guidelines that their patients may be contacted by study site recruiters to participate.

Depression: Primary care providers and psychiatric providers who manage the care of eligible patients will be identified, and may be approached by qualified study personnel, and given the opportunity to participate as a study provider. Providers will be notified per site institutional guidelines that their patients may be contacted by study site recruiters to participate.

### **6.2 Participant Consent Process**

Pre-screened participants that meet the inclusion criteria will be asked to provide an informed consent/assent.

Original informed consent documents will be maintained at the site. Copies of the signed informed consent will be given to the participant. The consenting process can be remote, via a phone or electronically if approved by the reviewing IRB.

### **6.3 Participant Discontinuation/Withdrawal from the Study**

Participants may stop participating and withdraw from the study at any time. All information and data collected up until that point will be used in the study.

If a participant wishes to withdraw consent, they should contact study staff. A participant may also revoke HIPAA authorization and must provide the revocation in writing. Study staff may attempt to obtain a reason for withdrawal from the participant and record it in the study database.

In the acute pain trial, the principal investigators or clinical site investigators may withdraw a participant from the study for any of these reasons:

- Participant does not have the surgery within 12 months of study enrollment
- Participant has the surgery at a healthcare system that is different from where the participant enrolled
- Participant's surgery is scheduled for a date after the close of the enrollment period for that clinical site
- Participant is unable to have the surgery for other medical reasons

